## Proposed research project

Title: A Double-Blinded, Randomized-Control-Trial to Investigate the Effect of Pulsed Electromagnetic Field (PEMF) for Patients with Knee Osteoarthritis

### Background:

Health care costs are increasing alarmingly, which will impose an overwhelming economic burden to an aging society like that of Hong Kong. For example, degenerative musculoskeletal disorders such as osteoarthritis (OA) present a grand challenge with its high prevalence (>40% in the elderly suffered from knee OA). OA is a debilitating progressive disease with typical symptoms such as acute pain causing loss of mobility Currently there is no cure for OA. Pharmacological treatment and new regenerative technologies such as stem cell therapy are actively being developed, but most of these options are very expensive per se, and side effects are not uncommon. Costeffectiveness is also a major consideration for devising new therapeutic modalities for OA.

PEMF treatment can modulate mitochondrial activities for muscle gain. Molecular processes are sensitive to the magnetic flux at extremely low frequency (<300 Hz), which are equivalent to the Earth's natural magnetic resonance (Schumann resonance). Applying magnetic fields at these low frequencies in the form of magnetic pulses, like a timely push to swing. The pulsing action will enhance the human magnetosensitive processes, which include the electron transport chain in mitochondria, calmodulin signalling and ion channels. The affected signal transduction pathways further influence the downstream myogenesis. (1) Therefore, a pulsed electromagnetic field (PEMF) may be a possible intervention to amplify molecular processes in favour of myogenesis. (2)

The therapeutic effects of PEMF in the field of orthopaedics have been recognized (4-6) and approved for clinical use for over the 40 years (3). The clinical evidences of the use of PEMF to treat knee OA has been summarized in Cochrane Reviews (7), suggesting that PEMF may provide moderate benefit for OA sufferers in terms of pain relief (8); but the improvements in function and quality of life (9) are not significant, probably due to persistent muscle weakness. Basic science studies revealed that PEMF can reduce cartilage degeneration (10), promote chondrogenesis in stem cells (11, 12), augment anabolic effect in OA chondrocytes (13) and cartilage explant (14), counteract inflammation (15), and improved subchondral bone quality (16, 17). However, large variations in treatment conditions still present major obstacles to optimize the therapeutic effects of PEMF, such as device parameters (PEMF frequency, amplitudes symmetry, field gradient) (18) and treatment regimen (duration of PEMF sessions, number of session and total treatment duration needed). Moreover, there is room for further improvements for PEMF treatment for OA patients with respect to function and quality of life. Our approach is unique in that we target muscle to act as a delivery system for regenerative agents that will promote healing, naturally.

Our study will examine the efficacy of PEMF treatment introduced at patient with Knee OA. Also, it helps to set up the treatment regime for the PEMF device to impose myogenic effects, including exposure time per session, the number of treatment sessions and the duration of treatment. To our best knowledge, this proposed study aims to apply PEMF as an intervention for patients with knee OA. In turn, it would be the first study to examine the effect of PEMF for patients with knee OA to relief in OA symptoms.

# Objective:

To conduct a double-blinded, randomized controlled trial to investigate the effect of PEMF treatment on knee pain for patients with knee OA.

### Hypothesis:

PEMF treatment may have a positive effect on increasing quadricep muscles strength. With the enhanced muscle strength and power, it may lead to relief in OA symptoms and improve knee functions.

### Setting:

The study will be carried out in the Department of Orthopaedics and Traumatology at Prince of Wales Hospital.

### Subject recruitment:

The study protocol will be in compliance with Declaration of Helsinki and ICH-GCP. Subjects will be recruited from the Department of Orthopaedics and Traumatology of Prince Wales Hospital in Hong Kong and patients who can meet all the inclusion criteria will be invited to participate in two sessions of assessments.

A total of 110 subjects and 20 matched non-Knee OA subjects will be recruited and follow up for 8 weeks. They will undergo 1:1 randomization into two study arms:

- 1. PEMF treatment
- 2. Control (Sham treatment)

Inclusion criteria:

- 1. Age 50 or above
- 2. Unilateral knee OA with Kellgren-Lawrence grade 2-3 by X-ray
- 3. Sedentary lifestyle (Tegner activity level  $\leq$  3)
- 4. No acute knee injuries in past 12 months
- 5. No muscle strain in past 12 months
- 6. No degenerative joint diseases in other joints except the involved knee

### Exclusion criteria:

- 1. Age smaller than 50 years old
- 2. Experienced any concomitant bone fracture, ACL injury, major meniscus injury
- 3. Any rheumatological diseases
- 4. Metal implants that would cause interference on MRI
- 5. Previous contralateral knee injury
- 6. Recent knee injections (prior 3 months)
- 7. Physical inability to undertake testing procedures
- 8. Pregnancy or possibility of pregnancy

#### **Outcome measures:**

#### Self-reported knee functions

The subjective functional outcome will be evaluated by the The Knee injury and Osteoarthritis Outcome Score (KOOS),International Physical Activity Questionnaire (IPAQ), and Tegner activity score:

1) The Knee injury and Osteoarthritis Outcome Score (KOOS)

It contains 42 items with 5 subscapes: pain, other symptoms, function in daily living (ADL), function in sport and recreation (Sport/Rec), and knee-related quality of life (QOL). It allows us to obtain information on how the patient's activities of daily living and overall quality of life is affected by the knee condition.

2) International Physical Activity Questionnaire (IPAQ)

The level of physical activities during the past 7 days will be evaluated with a validated Chinese version of the quantitative physical activity questionnaire.

3) Tegner activity score

This is an activity level scale from 1 (low activity) to 10 (high activity).

4) Short Form-36 questionnaires (SF-36)

It will be used to evaluate Health-Related Quality of Life.

Muscle strength assessment by hand-held dynamometer

Hand-held dynamometer microFET2 (Hoggan Scientific, Salt Lake City UT, USA) will be used to assess lower limb strength and power. Assessment of isometric muscle strength and power will be performed with the participants in a seated position to assess knee extensors and knee flexors. All tests will involve maximal voluntary isometric contractions. Instructions provided to participants for all trials will be 'at the count of three, push/pull as hard and as fast as you can and hold that contraction until I say relax' in Cantonese. Each test will last between three to five seconds and ended after a steady maximal force was produced by the subject. Constant verbal encouragement will be provided throughout the testing. Both limbs will be assessed to record side-to-side difference. Two trials were recorded for each muscle group.

### Posture assessment

Patients with knee OA demonstrated postural deficits during double leg squat on their affected and unaffected sides when compared with healthy controls (19). The centre of pressure (COP) excursion range in the anterior-posterior direction during squat can be used to monitor postural changes related to functional impairment in knee OA (20). In brief, the subjects will start with feet shoulder-width apart and arms outstretched and parallel to the ground on a pressure sensor mat (I-Scan, Tekscan, Boston, Massachusetts), then they will be instructed to squat down as low as possible and then rise to the upright position with their preferred pace while keeping their arms parallel to the ground. COP will be determined by the pressure sensor and presented as percentage of the longitudinal foot.

Static postural conditions include stand on double leg with open (DO) and close eyes (DC) for 30s and stand on one leg with open eyes (SO) for 10s. For DC condition, visual input will be eliminated by wearing a blindfold. During double leg stance, each subject will be asked to stand barefoot in a comfortable position (shoulder width apart) on the force-platform while positioning the arms on their sides. To prevent falls during the testing conditions, one of the experimenters stand beside patients. During single leg stance condition, the subjects will be asked to remain as motionless as possible while standing on the involved leg on the center of the platform, keep their eyes open and maintain the arms relaxed at their sides. In these cases, the failed trial will not be used in the data analysis. The patients will perform three trials of each condition. The conditions will be separated from each other by a 1 min rest time to minimize fatigue.

Dynamic postural control will be evaluated using the task of transitioning from double-leg to single-leg standing. The patients will be instructed to stand on a force plate with the load distributed as evenly as possible between the two legs and to keep looking straight ahead, with their feet shoulder-width apart and their arms folded across the chest. Then, the patients perform the transition from double-leg to single-leg standing as fast as possible after a verbal cue and will be asked to maintain single-leg standing as stably as possible for at least 5 s. The more affected limb will be tested in the single leg standing task. All patients will practice the task three times. Data collection starts when they become familiar with the task. Each patient will be allowed to rest at any time to prevent the effects of fatigue. Trials in which the patients fail to maintain single leg standing for at least 1 s will be excluded from the analysis. Three successful trials perform by each patient will be analyzed.

### Chair stand test

While seated in a custom-built chair allowing only the bare feet to exert force on a force plate (Tekscan, U.S.), the participant will perform trials of six STS cycles as fast as possible. The

seat height is 120% tibia length. The inter-feet distance is the width of the shoulders, the knee angle is 90°-100°, and the arms are placed across the chest. At least three approved trials will be performed after task familiarization. A trial will be approved if the knees are fully extended while standing, the back touches the backrest while seated, and the feet and hands retain their positions throughout the trial. To ensure maximal performance, an additional trial will be performed if the last approved trial is the fastest. The completion time will be calculated as the time-period from the 1st vertical ground reaction force peak of the first repetition to the first peak of the 6th repetition. Thus, it will reflect the time of five repetitions. The rate of force development will be determined as the mean slope of the rising force of the first force peak of each of the 2nd to the 6th repetition in the interval of 30–70% exerted peak force. Results are reported as the mean of the two fastest approved trials in body weight per second (BW/s).

## **Biochemical Assays**

Blood samples will be taken under non-fasting conditions. Serum / plasma obtained will be immediately stored at -80°C until analysis. Serum 25(OH) Vit-D assay: Serum 25(OH)Vit-D levels will be measured by commercial 25(OH) Vitamin D ELISA kit (Abcam ab213966) according to the manufacturer's instruction, providing the quantitative determination of 25(OH) Vitamin D3 and 25(OH) Vitamin D2. Sensitivity: 1.98 ng/ml (Range: 0.5 ng/ml - 1010 ng/ml).

Range of metabolites will also be evaluated. Human serum was vortexed with 500  $\mu$ L of acetonitrile with internal standard (25 ng/mL 25-hydroxyvitamin D3-d3 and 24R,25-dihydroxyvitamin D3-d6, 10 ng/mL 3-epi-25-hydroxyvitamin D3-d3, 5ng/mL 1 $\alpha$ ,25-dihydroxyvitamin D3) for 1 minutes and then stood in 4oC for 30 minutes. Proteins were precipitated and spun down by centrifugation for 15 min at 14,000×g. The supernatant was transferred into 2-mL tubes containing 400  $\mu$ L 0.4 M potassium hydrogen phosphate (K2HPO4) and vortexed for 30 seconds followed by the addition of 500  $\mu$ L methyl t-butyl ether (MTBE) for liquid–liquid extraction. The upper organic layer was transferred into 2-mL tubes for drying under the stream of nitrogen gas. The derivatized extract was derivatizated with 500  $\mu$ L 0.15 mg/mL 4-phenyl-1,2,4-triazoline-3,5-dione (PTAD) in acetonitrile at room temperature for 1 h and then stored overnight at +4 °C. The derivatized extract was dried under the stream of nitrogen gas and then redissolved with 30  $\mu$ L methanol. The resulting solution was subjected to UPLC-Qtrap/MS

# Serum myokine evaluation

Phlebotomy (5ml) will be performed on the day before PEMF treatment, and at 2-, 3-, 6- and 12- months after commencement of treatment. The serum will be prepared by centrifugation and kept in a -800 freezer until use. Quantitative analysis for myokines and proteins related to muscle metabolism will be performed by Human Myokine Magnetic Bead Panel (Millipore) with Bioplex-200 bead-based suspension assay system (LKSIHS core facilities), or enzyme-linked immunosorbent assay (ELISA). These include Brain-derived neurotrophic factor (BDNF), Fibroblast growth factor-21 (FGF-21), Interleukin-6 (IL-6), IL-15, Irisin, Myostatin (MSTN)/GDF8, Insulin-like growth factor 1 (IGF-1), FGF-2, IL-8, Follistatin, Musclin, Myonectin, Decorin, Meteorinlike, Osteopontin, Secreted protein acidic and rich in cysteine (SPARC), Klotho, Procollagen type III N-terminal peptide (P3NP), and C- terminal of troponin T1 (TNNT1).

### Visual Analogue Scale

The subjective measurement for chronic and acute pain will be recorded be Visual Analogue Scale (VAS). VAS is consisted of a 10-cm line which represent the continuum between "pain less" and "worst pain from 0 cm to 10 cm. Subject will be ask to draw a mark of it before and after the PEMF treatment.

# Study design

# Randomization and blinding

Participants will be randomized into 1:1 allocation. Blocked randomization will be undertaken based on the computer-generated allocation sequence, whereby 110 participants would be divided into blocks of 10 for 2 groups, Thereafter, the participants will use their key card to complete the assigned treatment regime, without knowing if the machine is delivering active or sham PEMF. Outcome assessors and trial administrators are blinded for the group allocation.

## Follow up time points

Subjects with OA knee will be recruited into this randomized controlled trial. Baseline assessments including KOOS, IPAQ, muscle strength, posture control and serum markers will be taken before PEMF treatments, and same set of measurements will be monitored at 1- and 2- months after the commencement of PEMF, and at 3-, 6- and 12- months after finish the PEMF intervention if possible.

## Sample size calculation:

KOOS Score will be employed as primary outcome for sample size estimation. The minimal clinically important change has been determined as 10 for KOOS (21). A repeated ANOVA will be used to compare KOOS scores, IPAQ, muscle strength, posture control and serum markers before PEMF treatment and at 1-, 2-months after the commencement of PEMF treatment, and at 3-, 6- and 12- months after finish the intervention. When the sample size is 34 per groups with 6 repeated measurements, a one-way analysis of variance will have 95% power to detect at the 0.05 level and change of 10 with a standard deviation of 15 KOOS score (22). An additional 35% will be added to account for possible attrition. Thus, 110 (55x2) subjects will be recruited in total.

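### The primary outcome is given only as the KOOS score: no subscale or combining rule, deciding visit or between-arm contrast is designated, and no pain measure is primary although the sole objective is knee pain

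*Protocol*

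**What the plan says.** **Primary outcome.** Protocol, Sample size calculation: "KOOS Score will be employed as primary outcome for sample size estimation". No other section names a primary outcome.

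**What KOOS is.** Protocol, Self-reported knee functions: "It contains 42 items with 5 subscapes: pain, other symptoms, function in daily living (ADL"), followed by sport and recreation and knee-related quality of life. No total, average or other combining rule is given.

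**Objective and hypothesis.** The Objective is to "investigate the effect of PEMF treatment on knee pain". The Hypothesis is wider: through gains in muscle strength, "it may lead to relief in OA symptoms and improve knee functions".

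**Comparisons.** Sample size calculation: "A repeated ANOVA will be used to compare KOOS scores, IPAQ, muscle strength, posture control and serum markers before PEMF treatment" and at five later visits. The same paragraph then bases the power on a one-way analysis of variance. Data processing and analysis names only the paired t test and the Wilcoxon signed rank test, and sets 0.05 for every test.

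**Visits.** Follow up time points lists baseline, 1 and 2 months after the start of treatment, "and at 3-, 6- and 12- months after finish the PEMF intervention if possible". Subject recruitment says that subjects "will be recruited and follow up for 8 weeks" and mentions two assessment sessions.

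**Other pain measure.** Visual Analogue Scale: "Subject will be ask to draw a mark of it before and after the PEMF treatment". It is not designated primary.

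**The concern.** A primary outcome should identify one variable, at one time, in one comparison. Here the variable could be any of five subscales or an undefined composite. The time could be any of five post-baseline visits or their average. The comparison could be a change over time or a difference between arms. KOOS ranks above the other outcomes, but nothing ranks the results within KOOS or across visits.

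Two things are at stake. First, the trial could report a positive primary result on, say, quality of life at one visit while pain is unchanged, and the protocol would not say whether the pain objective had been met. Second, the 95% power belongs to no designated endpoint, so a reader cannot tell what the 110 subjects are powered to show.

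**Working it through.** **Inputs from the protocol (Sample size calculation).** Difference 10, SD 15, alpha 0.05, 34 per group, six measurements, 95% power, 35% attrition, 55 per arm recruited. The correlation between measurements, the sidedness of the test, and whether 15 is the SD of a score or of a change are not stated. Below, all tests are two-sided, power comes from the noncentral t distribution, and correlations (ρ) are assumptions. The standardised difference is d = 10/15 = 0.667.

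**1. Reproducing the stated 95% at 34 per group**

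(a) *Arm difference averaged over all six measurements.* SD of the mean = 15·√((1+5ρ)/6). At ρ = 0.5 this is 15·√(3.5/6) = 11.46. The noncentrality is 10/(11.46·√(2/34)) = 3.60 on 66 df, and power is 94.4%. At ρ = 0.3 and 0.7 it is 98.7% and 87.8%. This version counts the 10-point difference at baseline too. With no difference at baseline and 10 points at the five later visits, the mean difference is 10·5/6 = 8.33, the noncentrality at ρ = 0.5 is 3.00, and power is 84.0%.

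(b) *Within-arm paired change, taking 15 as the SD of change.* Noncentrality = 0.667·√34 = 3.89 on 33 df; power is 96.5%. No correlation is needed, but this does not compare PEMF with sham.

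(c) *Unadjusted arm difference at one visit.* Noncentrality = 0.667·√(34/2) = 2.75 on 66 df; power is 77.3%.

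| Contrast at 34 per group | Power |
|---|---|
| Arm difference, mean of six, ρ = 0.5 | 94.4% |
| Same, no difference at baseline | 84.0% |
| Within-arm paired change, SD of change 15 | 96.5% |
| Arm difference at one visit, unadjusted | 77.3% |

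Readings (a) and (b) both land near 95%, so the stated figure does not reveal which was meant.

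**2. False-positive chance if any one of five subscales could count**

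This is an illustration; the protocol states no such rule. Under independence the chance is 1 − 0.95⁵ = 22.6%. For five jointly normal test statistics with a common correlation:

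| Assumed correlation | 0.3 | 0.5 | 0.7 | 0.8 | 0.9 |
|---|---|---|---|---|---|
| At least one p < 0.05 | 21% | 18% | 15% | 13% | 10% |

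One score tested once gives 5%.

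**3. Power for one designated endpoint**

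Example: PEMF minus sham in KOOS Pain at 2 months, adjusted for baseline, assuming that 10 and 15 carry over to that subscale. Residual SD = 15·√(1−ρ²), where ρ is the correlation with baseline; df = 2n − 3. At ρ = 0.5 the SD is 12.99, so the noncentrality is 3.17 at n = 34 and 4.04 at n = 55.

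| Per arm | ρ = 0.3 | ρ = 0.5 | ρ = 0.7 | Unadjusted |
|---|---|---|---|---|
| 55 | 95.3% | 97.9% | 99.8% | 93.4% |
| 34 | 81.0% | 87.8% | 96.6% | 77.3% |

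For 95% power the evaluable number per arm is 55, 45 and 31 at ρ = 0.3, 0.5 and 0.7. From 55 recruited, that tolerates losses of 0%, 1 − 45/55 = 18% and 1 − 31/55 = 44%.

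**The case against.** **The text is less open than it may look.** Eight weeks of follow-up, two assessment sessions, paired tests, a VAS marked before and after treatment, and later visits only where possible all point towards baseline versus end of treatment. This stands as a hint. But the same protocol plans six KOOS measurements and builds its power statement on them, and no section makes end of treatment the deciding visit.

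**Comparisons are named.** A reader might infer that the protocol has no contrast at all. That is too strong: it names a repeated ANOVA, a one-way ANOVA and paired tests. They do not agree, and none is explicitly between arms. A reader might also infer that the 95% can be checked only by supplying an unstated correlation. That is not so: the paired reading gives 96.5% without one, provided that 15 is the SD of change.

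**KOOS covers pain.** It has a pain subscale, and the hypothesis extends to symptoms and function, so KOOS is a defensible instrument. What is missing is a statement of which part decides.

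**The VAS is not in the follow-up list.** Little should be made of this. The list is introduced as including certain measures, other instruments are also absent from it, and the VAS has its own timing.

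**22.6% is not the trial's error rate.** Agreed. It assumes an any-subscale rule that the protocol does not state, and independence that is implausible for subscales of one questionnaire.

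**A statistical analysis plan could settle this.** It could set the model and the handling of multiplicity. Which measure and visit are primary is a design decision that the protocol itself makes, incompletely, and leaves unaligned with its own objective.

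**Conclusion.** The point holds in this form: the protocol designates KOOS as primary without a subscale or combining rule, a deciding visit or an explicit between-arm contrast, and designates no pain measure as primary against an objective of knee pain.

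The consequence is several candidate primary results with no rule for choosing between them. At 34 per group the stated inputs give 77% to 96.5% across the readings tabulated at ρ = 0.5, and up to 98.7% for the six-measurement average at ρ = 0.3. The false-positive illustration runs from about 10% to 21%, with 22.6% as its ceiling, and applies only if any subscale could count as success.

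This does not show that the sample size arithmetic is wrong: two readings come close to the stated 95%. Nor does it show that the trial intends to claim success on whichever subscale is significant; the text is silent on that. All correlations are assumptions. The defect should be corrected, and the correction is cheap.

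**What to change.** Name one primary endpoint that matches the objective. For example: the PEMF-minus-sham difference in KOOS Pain at 2 months (end of the 8-week treatment), adjusted for baseline and tested once at two-sided 0.05. Other choices are possible if justified. Make the remaining KOOS subscales, the other visits, VAS, strength, posture and serum markers secondary or exploratory, and confine the confirmatory 0.05 claim to the primary test. Keep 110 subjects and restate the power for that endpoint, giving its SD, the assumed baseline correlation and the visit to which the 35% attrition refers.

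The cost: no new visit or measurement is needed, but function and the other subscales can no longer be claimed as primary. If attrition leaves only 34 evaluable per arm at 2 months, power is about 81% to 97% for ρ from 0.3 to 0.7, so the stated 95% may have to be lowered. Keeping the sample at 110 means accepting that, or showing that the correlation is high or the losses by 2 months are smaller.

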### Data processing and analysis:

The data obtained in the tests will be analysed using Statistical Package for Social Science (SPSS) (IBM SPSS ver.26). For parametric data, paired sample t test will be used. Wilcoxon signed rank test will be used to analyse the data sets if they are non-parametric. The alpha level will be set at 0.05 for all statistical tests.

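### The only stated rule for non-normal outcomes is a within-person signed rank test, so IPAQ and the serum markers may get no PEMF-versus-sham comparison

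*Protocol*

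**What the plan says.** Two sections of the protocol describe the analysis.

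- **Sample size calculation.** "A repeated ANOVA will be used to compare KOOS scores, IPAQ, muscle strength, posture control and serum markers before PEMF treatment". Five later visits complete the sentence. It names neither the scale of analysis nor the arm term. The power statement that follows concerns KOOS alone: "When the sample size is 34 per groups with 6 repeated measurements", the design is said to "have 95% power to detect at the 0.05 level and change of 10 with a standard deviation of 15 KOOS score".
- **Data processing and analysis.** One rule covers data that suit a parametric test: "For parametric data, paired sample t test will be used". The other covers everything else, and is equally short: "Wilcoxon signed rank test will be used to analyse the data sets if they are non-parametric". A single significance level applies throughout: "The alpha level will be set at 0.05 for all statistical tests". No between-arm test and no transformation is named here.

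The serum outcomes are set out under Serum myokine evaluation: "Quantitative analysis for myokines and proteins related to muscle metabolism will be performed by Human Myokine Magnetic Bead Panel" or by ELISA, with 19 proteins listed. Biochemical Assays adds vitamin D and its metabolites. Under Outcome measures, IPAQ is a quantitative record of the past seven days' activity. Participants are randomized 1:1 to PEMF or sham.

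**The concern.** The trial is randomized so that PEMF can be compared with sham. A paired t test or a signed rank test asks a different question: did people in one group change between two visits? Change within an arm mixes any effect of the device with placebo response, natural course, regression to the mean and repeat-testing effects. Only the contrast between arms removes these.

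The rule matters most for the serum markers and IPAQ. Concentrations and activity totals cannot be negative, and the trial enrols sedentary people, so right-skewed values are plausible. An analyst who finds them non-normal and follows the protocol literally would leave the repeated ANOVA for the signed rank test, and would report before/after results separately by arm. The serum panel is the direct evidence for the protocol's rationale that muscle releases regenerative factors, so that evidence could end up without a randomized comparison.

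A second, smaller issue is efficiency. If skewed markers stay in the ANOVA untransformed, a few high values can dominate the error term.

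**Working it through.** **1. The plan's own figure.** Inputs from Sample size calculation: 34 per group, 6 measurements, difference 10, SD 15, alpha 0.05 (two-sided assumed). The within-person correlation is not stated; 0.5 is assumed.

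- Between-group test in repeated measures: f = 10/(2 × 15) = 0.333; λ = f² × N × m / (1 + (m − 1)ρ) = 0.1111 × 68 × 6 / 3.5 = 12.95. Power is 94.4%, close to the stated 95%.
- Paired t test, n = 34, taking 15 as the SD of change: noncentrality = (10/15) × √34 = 3.89. Power is 96.5%, also close.
- Attrition ("An additional 35% will be added to account for possible attrition"): 34/0.65 = 52.3, so 53 per arm, near the planned 55. Expected completers: 55 × 0.65 = 35.75, about 36 per arm.

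The KOOS figure is therefore reproducible, under either a between-arm or a paired reading. It says nothing about power for IPAQ or serum markers, which have no SD, CV or effect size in the protocol.

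**2. What the signed rank test shows when PEMF does nothing.** Both arms are given the same true change of 0.4 SD (an assumption). The test is run within one arm, 2,000 simulated trials per setting.

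| Common change (SD units) | Significant, n = 34 | Significant, n = 55 |
|---|---|---|
| 0 | 4% | 5% |
| 0.2 | 20% | 30% |
| 0.4 | 61% | 81% |
| 0.5 | 80% | 95% |

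Comparing the two within-arm p values does not rescue the result. The arms are independent, so the chance of PEMF significant and sham not is p(1 − p): 0.612 × 0.388 = 24% at n = 34, and 0.808 × 0.192 = 16% at n = 55, with no difference between the arms. A valid between-arm test at the 0.05 level would reject in about 5% of such trials in total, in both directions together.

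**3. Log scale against untransformed scale, both between arms.** Assumptions: log-normal marker with log SD s, so CV = √(exp(s²) − 1); multiplicative effect set for 80% power on the log scale. For one visit, δ = s × √(2/n) × (1.96 + 0.84). Example: s = 0.8, n = 55 gives 0.8 × 0.1907 × 2.80 = 0.427, a ratio of 1.53. For the mean of six visits (ρ = 0.5), s is multiplied by √((1 + 5 × 0.5)/6). For the change score with log correlation r, s is multiplied by √(2(1 − r)). There were 4,000 runs per setting for the first two designs and 6,000 for the change score.

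Untransformed power, %:

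| CV | One visit, n = 34 / 55 | Six-visit mean, n = 34 / 55 | Change score, n = 36, r = 0.5 / 0.7 |
|---|---|---|---|
| 0.31 | 78 / 78 | 77 / 79 | 81 / 81 |
| 0.53 | 75 / 73 | 76 / 76 | 78 / 76 |
| 0.95 | 67 / 67 | 71 / 71 | 70 / 66 |
| 1.31 | 60 / 61 | 67 / 66 | 62 / 57 |
| 1.79 | 53 / 54 | 60 / 61 | 54 / 48 |

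Simulated log-scale power was 78–81% throughout. Untransformed type I error in the one-visit setting stayed at about 4–6%.

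**The case against.** Four fair points can be made for the plan.

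- **The scale is not stated.** A reader might infer that the protocol commits to a raw-scale ANOVA. It does not: it names no scale and excludes no transformation, and a statistical analysis plan could settle this. The point stands, so silence on scale is not the finding.
- **A ratio is not ruled out.** A reader might conclude that no PEMF-to-sham ratio could be reported. Log values can enter the same repeated ANOVA and be back-transformed. What is true is narrower: neither paired test, as written, gives one.
- **The skew and its cost are assumed.** No distribution is given for any marker or for IPAQ, and the simulation makes the log scale correct by construction. This stands. The loss is negligible near CV 0.3 and material only from about 0.5–1 upward, and validity is not at risk.
- **The paired tests may be meant for something else.** Signed rank does not literally discard the sham arm, since it can be run in each arm. The protocol does not call it a fallback for the ANOVA, and the before/after VAS reading could be its intended use. But the data analysis section limits neither paired test to VAS; it applies them to the data obtained in the tests generally.

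It is also fair that the defect is not special to markers. The paired t test raises it for KOOS, strength and posture too. That widens the problem and does not remove it here.

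**Conclusion.** The concern holds in a limited form. The protocol writes down one rule for non-normal data, and that rule does not compare the randomized arms. Followed literally, it leaves IPAQ and the serum markers with before/after results only. This follows from the text and needs no assumption about CVs. The 61% and 81% figures illustrate how misleading such a result could be, and rest on an assumed common change of 0.4 SD.

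The efficiency argument is secondary and conditional. Across the three designs checked, untransformed power against 80% on the log scale is about 77–81% at CV 0.3, 73–78% at CV 0.5, 66–71% at CV 0.95, 57–67% at CV 1.3 and 48–61% at CV 1.8. The documents do not show where the markers fall in this range, so a definite loss of power cannot be claimed.

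These outcomes did not drive the sample size. The correction is worth making, but for them it does not threaten the planned trial size.

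**What to change.** In Data processing and analysis:

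1. Replace the signed rank rule with a between-arm analysis, and reconcile the paired t test with the repeated ANOVA in Sample size calculation for all outcomes, KOOS included. If paired tests are kept, label them as descriptive within-arm summaries.
2. Serum markers and vitamin D metabolites: log-transform, include log baseline as covariate, and report PEMF:sham ratios of geometric means with 95% CIs.
3. IPAQ: use a rank-based between-arm ANCOVA adjusted for baseline. Adding one and taking logs is less suitable, because the result depends on the unit and a cluster of values near zero would remain.
4. Fix these choices before unblinding, so that scale is not chosen marker by marker from the results.

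The cost is wording and a transformation step, with no new data or visits. Serum effects will be read as ratios instead of concentration differences. For markers with low CV the log scale gains little, but it also loses little.
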